Scenarios of exposure during breastfeeding must be reported, irrespective of the presence of an associated AE. An exposure during breastfeeding report is not created when a Pfizer drug specifically approved for use in breastfeeding women (eg, vitamins) is administered in accord with authorized use. However, if the infant experiences an AE associated with such a drug's administration, the AE is reported together with the exposure during breastfeeding.

Medication error

A medication error is any unintentional error in the prescribing, dispensing or administration of a medicinal product that may cause or lead to inappropriate medication use or patient harm while in the control of the health care professional, patient, or consumer. Such events may be related to professional practice, health care products, procedures, and systems including: prescribing; order communication; product labeling, packaging, and nomenclature; compounding; dispensing; distribution; administration; education; monitoring; and use.

Medication errors include:

- Near misses, involving or not involving a patient directly (eg, inadvertent/erroneous administration, which is the accidental use of a product outside of labeling or prescription on the part of the healthcare provider or the patient/consumer);
- Confusion with regard to invented name (eg, trade name, brand name).

The investigator must submit the following medication errors to Pfizer, irrespective of the presence of an associated AE/SAE:

- Medication errors involving patient exposure to the product, whether or not the medication error is accompanied by an AE.
- Medication errors that do not involve a patient directly (eg, potential medication errors or near misses). When a medication error does not involve patient exposure to the product the following minimum criteria constitute a medication error report:
 - An identifiable reporter;
 - A suspect product;
 - The event medication error.

Overdose, Misuse, Extravasation

Reports of overdose, misuse, and extravasation associated with the use of a Pfizer product are reported to Pfizer by the investigator, irrespective of the presence of an associated AE/SAE.

Lack of Efficacy

Reports of lack of efficacy to a Pfizer product are reported to Pfizer by the investigator, irrespective of the presence of an associated AE/SAE or the indication for use of the Pfizer product.

Occupational Exposure

Reports of occupational exposure to a Pfizer product are reported to Pfizer by the investigator, irrespective of the presence of an associated AE/SAE.

11.1. Single Reference Safety Document

The Summary of Product Characteristics for Xeljanz® will serve as the single reference safety document during the course of the study, which will be used by Pfizer safety to assess any safety events reported to Pfizer Safety by the investigator during the course of this study.

The Single reference safety document (SRSD) should be used by the investigator for prescribing purposes and guidance.

12. PLANS FOR DISSEMINATING AND COMMUNICATING STUDY RESULTS

Final study results are planned to be published in peer-reviewed journals and presented in national congresses.

Pfizer has no objection to publication by Investigator of any information collected or generated by Investigator. However, to ensure against inadvertent disclosure of Confidential Information or unprotected Inventions, Investigator will provide Pfizer an opportunity to review any proposed publication or other type of disclosure before it is submitted or otherwise disclosed.

Investigator will provide manuscripts, abstracts, or the full text of any other intended disclosure (poster presentation, invited speaker or guest lecturer presentation, etc.) to Pfizer at least 30 days before they are submitted for publication or otherwise disclosed. If any patent action is required to protect intellectual property rights, Investigator agrees to delay the disclosure for a period not to exceed an additional 60 days.

Investigator will, on request, remove any previously undisclosed Confidential Information (other than the Study results themselves) before disclosure.

If the Study is part of a multi-centre study, Investigator agrees that the first publication is to be a joint publication covering all centers. However, if a joint manuscript has not been submitted for publication within 12 months of completion or termination of the Study at all participating sites, Investigator is free to publish separately, subject to the other requirements of this Section.

For all publications relating to the Study, Institution will comply with recognized ethical standards concerning publications and authorship, including Section II - "Ethical Considerations in the Conduct and Reporting of Research" of the Uniform Requirements for Manuscripts Submitted to Biomedical Journals, <http://www.icmje.org/index.html#authorship>, established by the International Committee of Medical Journal Editors. Publication of study results is also provided for in the Clinical Study Agreement between Pfizer and the institution. In this section entitled **Plans For Disseminating and Communicating Study Results**, the defined terms shall have the meanings given to them in the Clinical Study Agreement.

COMMUNICATION OF ISSUES

In the event of any prohibition or restriction imposed (eg, clinical hold) by an applicable Competent Authority in any area of the world, or if the investigator is aware of any new information which might influence the evaluation of the benefits and risks of a Pfizer product, Pfizer should be informed immediately.

In addition, the investigator will inform Pfizer immediately of any urgent safety measures taken by the investigator to protect the study patients against any immediate hazard, and of any serious breaches of this NI study protocol that the investigator becomes aware of.

ANNEX 2. ADDITIONAL INFORMATION

Not applicable.

A1.1 Definition and use of visit windows in reporting	34
A1.2 Definitions of bDMARDS and CSDMARDS	34
11.2. APPENDIX 2: HAQ ScORING GUIDELINEs.....	36

LIST OF TABLES

Table 1. Schedule of Activities.....	10
Table 2. EQ-5D.....	18
Table 3. EQ-5D weightings	19
Table 4. FACIT-Fatigue	20

LIST OF FIGURES

Figure 1. Study Design	9
-------------------------------------	---

LIST OF ABBREVIATIONS

Abbreviation	Definition
ACPA	Anti-citrullinated protein antibodies
AE	Adverse Event
CDAI	Clinical Disease Activity Index
CRP	C-Reactive Protein
csDMARD	Conventional synthetic Disease Modifying Antirheumatic Drugs
DAS	Disease Activity Score
DMARD	Disease Modifying Antirheumatic Drugs
EQ-5D	EuroQol five dimensions questionnaire
ESR	Erythrocyte sedimentation rate
FACIT	Functional Assessment of Chronic Illness Therapy
HAQ-DI	Health Assessment Questionnaire – Disability Index
JAK	Janus kinase (JAK)
LDL	Low-density lipoprotein,
MTX	Methotrexate
MMRM	Mixed model repeated measures
NI	Non-Interventional
NRI	Non-responder Imputation
PhGA	Physician's Global Assessment
PRO	Patient reported outcome

PFIZER CONFIDENTIAL

PtGA	Patient's global assessment of health
RA	Rheumatoid arthritis
RF	Rheumatoid Factor

Abbreviation	Definition
SAE	Serious Adverse Events
SAP	Statistical Analysis Plan
SAS	Statistical Analysis Software
SD	Standard deviation
SDAI	Simplified Disease Activity Index
SJC	Swollen joint count
TJC	Tender joint count
VAS	Visual Analogue Scale
WPAI	Work Productivity and Activity Impairment

1. AMENDMENTS FROM PREVIOUS VERSION(S)

This is the first version of the statistical analysis plan (SAP). There are no changes to the analyses specified in the protocol.

2. INTRODUCTION

This SAP is based on protocol A3921342 Protocol Version 2 dated 14th January 2020

Note: in this document any text taken directly from the non-interventional (NI) study protocol is *italicised*.

Rheumatoid arthritis (RA) is a chronic, autoimmune disease characterized by joint inflammation and destruction, leading to progressive disability and adverse psychological effects with severe impact on patients' quality of life.

The chronic nature of the disease deems necessary the long-term use of medication. Thus, RA represents significant health and socioeconomic burdens for the individual subject, healthcare systems and society, with indirect costs (productivity loss, absenteeism/disability, early retirement) accounting for up to ¾ of total costs for working patients.

As there is currently no cure for RA, the target of treatment strategies is to control disease activity, alleviate signs and symptoms, maintain physical function, optimize quality of life, reduce the rate of joint damage, and, if possible, induce and maintain complete remission. Although there are several effective treatments available nowadays, mainly biologic DMARDs, many patients fail to achieve or maintain the desired response and are treated sequentially with different drugs leading to increased costs, risk of toxicity and suboptimal effectiveness. Therefore, the ambition for personalized treatment has emerged and investigation to identify predictive tools of treatment response is a highly active area of research.

Tofacitinib (CP-690,550) is an oral Janus kinase (JAK) inhibitor that targets inflammation by reducing pro-inflammatory cytokine signaling and production.

The efficacy and safety evaluation of Tofacitinib for the treatment of RA is based on a comprehensive clinical development program including six randomized, double blind, multicenter phase III studies in adult subjects with active rheumatoid arthritis (RA). In these trials Tofacitinib consistently reduces signs and symptoms of RA, improves physical function and other subject-reported outcomes such as fatigue, pain and health-related aspects of quality of life in subjects with moderate to severe RA. Combined with its inhibition of the progression of structural damage, the development program has demonstrated Tofacitinib as an effective targeted synthetic disease-modifying antirheumatic drug (DMARD) in treating RA.ⁱ Long-term extension and Phase 3b/4 post authorization safety studies are aimed to demonstrate sustained efficacy and a consistent safety profile as seen in the Phase 2 and 3 controlled clinical trials.

However, these trials may have limitations reflecting real world situations. It has been estimated that only 21-33% of patients documented in registries, reflecting more accurately routine care, would have met eligibility criteria of major trials as they often exclude patients with co-morbidities. Also treatment of patients in daily clinical practice may vary from strict regulations in clinical trials. Therefore additional long-term data in registries and non-interventional studies of a European population would be helpful to further assess treatment outcomes in a real-world setting.

Furthermore, studies exploring the association between clinical and biochemical parameters with the efficacy of Tofacitinib treatment are scarce. Prior, analyses based on P123 and LTE Tofacitinib data have shown: a) early achievement of clinical disease control seems to determine longer term treatment effect with Tofacitinib in MTX-naïve patients; b) Tofacitinib treatment response at 6m may be higher for patients with higher disease activity at baseline based on CRP levels particularly for those with inadequate response to biologic DMARDs.. These results point out the need for more research and further investigation in order to help identify biomarkers that can predict response to Tofacitinib treatment in patients with RA.

The impact of RA on work can be profound since permanent work disability (inability to continue working), is common among patients with RA. In addition to the consequences for the patient, such as a decreased quality of life, work disability also leads to high costs. It is estimated that approximately one-third of the total cost for patients with RA is caused by production losses. This implies that at-work productivity loss is an important concern, since work hours are not only lost incidentally through sick leave, but also more structurally and profoundly by at-work productivity loss. As so far data on the impact of Tofacitinib on work productivity are still limited, this study will assess the effect Tofacitinib on work productivity and non-work activities.

2.1. Study Design

This is a 24-month, prospective, non-interventional, multi-center study with primary aim to identify clinical and/or biochemical factors that predict achievement of remission or Low Disease Activity (LDA) in patients with RA treated with Tofacitinib in Greece.

Eligible subjects will be followed from the date of first Tofacitinib prescription until study end, death, or discontinuation, or loss to follow-up (whichever comes first) for the occurrence of the endpoints of interest.

In this study, the medicinal product(s) are prescribed in the usual manner in accordance with the terms of the marketing authorisation.

The assignment of the patient to a particular therapeutic strategy is not decided in advance by this protocol, but falls within current practice and the prescription of the medicine should be clearly separated from the decision to include the patient in the study.

No additional diagnostic or monitoring procedures will be applied to the patients and follow-up visits are captured as part of normal medical practice. Epidemiological methods will be used for the analysis of collected data.

Figure 1. Study Design

[figure not shown]

Table 1 shows the key assessments and their associated time-points for data collection.

Table 1. Schedule of Activities

Study Week	Baseline (Enrolment)	Month 3	Month 6	Month 12
Visit Number	1	2	3	4
Informed Consent	x			
Anamnesis / Medical History	x			
Demographic data	x			
Educational level	x			
Working status	x			x
Inclusion/exclusion criteria	x			
Vaccination status	x			
Treatment/Medication				
Prior RA drug treatment	x			
Concomitant RA drug treatment	x	x	x	x
Co-medication	x	x	x	x
Safety				
Inflammatory markers	x	x	x	x
Documentation of Comorbidities	x			
Documentation of AE		x	x	x
Efficacy				

Number of swollen and tender joints	X	X	X	X
Morning stiffness	X	X	X	X
Patients Global Assessment of Arthritis	X	X	X	X
Physicians Global Assessment of Arthritis	X	X	X	X
Patient Assessment of Arthritis Pain	X	X	X	X
Health Assessment Questionnaire – Disability Index (HAQ-DI)	X	X	X	X
EuroQol EQ-5D Health State Profile	X	X	X	X
Work Productivity and Activity Impairment (WPAI) Questionnaire	X	X	X	X
FACIT (Functional Assessment of Chronic Illness Therapy) – Fatigue	X	X	X	X
Overall satisfaction with treatment	X			X
Medical visits		X	X	X
Diagnostic tests		X	X	X
Hospitalizations		X	X	X

PFIZER CONFIDENTIAL

Final Version 1.0

28-Jan-2020

Page 10 of 36

2.2. Study Population

The study population consists of patients with RA treated with Tofacitinib in Greece. *Overall, about 200 patients in 19 centres are to be included in this non-interventional study.*

The planned recruitment period is 12 months. With a planned observation duration of 12 months per patient, the entire study would thus last for 24 months. A patient will be followed up until the end of the planned study duration, regardless of any missing intermediate visits, as well as treatment changes during the course of follow-up.

2.3. Treatment/cohort labels

The treatment labels for analyses are as follows:

Treatment	Treatment Label
Tofacitinib (as monotherapy and combination)	Tofacitinib

2.4. Study Objectives

The primary objective of this study is to identify clinical and/or biochemical factors that predict achievement of remission or LDA in patients with RA treated with Tofacitinib.

Logistic regression will be used to investigate the impact of potential predictive factors on remission or LDA at month 6 of treatment.

The secondary objectives of the study are:

- *To describe the treatment patterns of RA patients prescribed Tofacitinib in a realworld setting;*
- *Assess the effect of treatment on patient quality of life and physical function;*
- *Estimate resource utilization and costs in patients with rheumatoid arthritis (RA) treated with Tofacitinib in Greece.*

The secondary objectives will be assessed using descriptive methods unless otherwise stated. Quality of life, measured using the EQ-5D, Functional Assessment of Chronic Illness Therapy (FACIT)-Fatigue Scale and the Work Productivity and Activity Impairment (WPAI) questionnaire, will be analysed using mixed model repeated measures (MMRM) models.

3. INTERIM ANALYSES

An interim analysis will not be performed in this study.

4. HYPOTHESES AND DECISION RULES

This study is **CCI** with no treatment comparisons. There are no formal hypotheses or decision rules.

5. ANALYSIS SETS/POPULATIONS

5.1. Full Analysis Set

The Full Analysis Set is defined as patients who receive at least one dose of Tofacitinib and have at least one set of post-baseline measurements. This population will be used for all efficacy analysis.

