9.5. Study Size

The primary objective of this study is to identify factors predictive of remission or LDA at month 6 of treatment. This will be investigated using a logistic regression model. For the purposes of the sample size, we will consider the LDA response rate.

Peduzzi et al suggest that such an analysis requires at least 10 events (ie, responders) per variable proposed in the model. The minimum number of subjects to include in the study can therefore be estimated using the following formula:

$$N = 10 k/p$$

where p is the smallest of the proportions of responders or non-responders in the population and k the number of covariates.

Based on the results of previous studies, eg, A3921187 we would expect an LDA response rate of 50% at 6 months and assuming that the primary analysis will include ten covariates, it will be necessary to observe 100 events in approximately 200 patients (ie, 100 events/0.50).

It is expected that the amount of missing data and drop-outs will be minimal in this study, so no allowance has been made for this in the sample size calculation.

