9.7. Data Analysis

This section gives an overview of the key methods and derivations required for the study. Detailed methodology for summary and statistical analyses of data collected in this study will be documented in a Statistical Analysis Plan (SAP), which will be dated, filed and maintained by the sponsor. The SAP may modify the plans outlined in the protocol; any major modifications of primary endpoint definitions or their analyses would be reflected in a protocol amendment. SAS (Version 9.1 or above) will be used for all analyses.

Unless specified otherwise, continuous variables will be summarised using descriptive statistics (n, mean, SD, median, min, max) and discrete variables will be summarised using counts and percentages.

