9.7.1. Analysis Populations

The Full Analysis Set is defined as patients who receive at least one dose of Tofacitinib and have at least one set of post-baseline measurements. This population will be used for all efficacy analysis. Details of any methods employed to deal with missing data will be outlined in the SAP.

The Safety Analysis Set is defined as all patients who receive at least one dose of Tofacitinib. This population will be used for all safety analysis.

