9.7.2. Safety Analysis

Adverse events will be reviewed and summarized on an ongoing basis during the study to evaluate the safety of subjects. Safety data will be presented in tabular and/or graphical format and summarized descriptively, where appropriate.

Medical history and physical examination information collected during the course of the study will not be captured for inclusion into the study database, unless otherwise noted. However, any untoward findings identified on physical examinations conducted after the administration of the first dose of study medication will be captured as an adverse event, if those findings meet the definition of an adverse event. Data collected at Screening that is used for inclusion/exclusion criteria, such as laboratory data, ECGs and vital signs will be considered source data, and will not be captured for inclusion into the study database, unless otherwise noted. Demographic data collected at Screening will be included in the study database.

Adverse events will be reported according to the 3-tier approach.

Reasons given for premature discontinuation will also be summarized.

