8.2.1. BACKGROUND AND DEMOGRAPHIC CHARACTERISTICS AND STUDY DISPOSITION

The Demographic and baseline variables will be summarised:

Continuous: Mean, SD, median, minimum and maximum

Categorical: Frequency and Percentage of population.

This will include age, sex, height, weight, smoking history, smoking status, educational level, social status, severity of disease, medical history (including RA diagnosis, RF and ACPA, presence of erosions on x-rays, presence of extra-articular manifestations [anemia, RA nodules, RA related vasculitis, amyloidosis or other]), vaccination status, hepatitis and tuberculosis status, comorbidities, co-medication and concomitant medication.

The number and percentage of patients at each time point will be provided along with reasons for withdrawal from the study. For patients who have discontinued Tofacitinib treatment but remain in the study information on the treatments prescribed following study treatment (Tofacitinib) will be listed.

These summaries will be based on the Full Analysis Set.

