8.2.3. Efficacy/Effectiveness Analyses

Analyses of the efficacy/effectiveness endpoints will be based on the FAS.

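### Month 3 changes in LDL and haemoglobin are candidate covariates in models meant for baseline predictors; as a smaller matter, treated patients with no post-baseline set fall outside the responder analysis

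*SAP*

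**What the plan says.** **Covariates.** Protocol 8.1.1 sets the primary aim as finding baseline characteristics that predict remission or LDA at Month 6. Protocol 9.7.3.1 and SAP 8.1.1 both describe the candidate predictors as baseline clinical and biochemical parameters. Protocol 9.7.3.1 lists LDL and haemoglobin among them without a later time point. SAP 6.4 defines these two, alone among the listed factors, as the change from baseline to Month 3. SAP 1 says that nothing differs from the protocol's analyses. Protocol 9.7 says that "any major modifications of primary endpoint definitions or their analyses would be reflected in a protocol amendment".

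**Selection.** Each factor is tested alone. Those with p below 10%, plus any thought clinically important, enter a multivariate model that is reduced backward at 5% (SAP 8.1.1).

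**Population.** SAP 5.1 defines the Full Analysis Set (FAS) as "patients who receive at least one dose of Tofacitinib and have at least one set of post-baseline measurements". Protocol 9.7.1 has the same definition and adds "This population will be used for all efficacy analysis". SAP 8.2.3 repeats it: "Analyses of the efficacy/effectiveness endpoints will be based on the FAS". Neither document says what makes up a set. For the baseline, disposition and withdrawal summaries, SAP 8.2.1 says "These summaries will be based on the Full Analysis Set". Protocol 9.7.2 states, under safety, "Reasons given for premature discontinuation will also be summarized".

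**Missing outcomes.** Protocol 9.7.3.1 applies non-responder imputation (NRI) to patients with missing data at Month 6. SAP 7 applies it only when every DAS28-4 (CRP) component is missing. Otherwise it carries the absent components forward from the last post-baseline value. SAP 7 gives no rule for missing covariates.

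**The concern.** A change measured three months into treatment is not known when tofacitinib is prescribed and may itself be part of the response. It cannot serve as a baseline predictor. If it is entered alongside true baseline factors, it can also absorb part of their association with the outcome. The study's product is a list of baseline predictors with odds ratios, so this affects the primary result directly.

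There is a second cost. The change cannot be computed without a Month 3 laboratory value. Fitting on complete records, the usual default when no rule is given, removes such patients from any model that contains the term. Protocol 9.9 itself warns that individual items are more likely to be missing in usual care.

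The FAS raises a related but smaller question. Someone treated and then never assessed again is left out of the responder analysis, where NRI would have counted that person as a non-responder. SAP 8.2.1 does not describe such patients either, because its summaries use the same set.

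**Working it through.** **1. The plan's own size.** Protocol 9.5 uses N = 10k/p with k = 10 covariates and p = 0.50. This gives N = 10 × 10 / 0.50 = 200 patients and 200 × 0.50 = 100 responders, as stated. No allowance is made for loss.

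**2. Month 3 terms.** Let m be the share without a Month 3 change in LDL or haemoglobin. The documents give no value, so m is assumed, and missingness is taken as unrelated to response. Responders left = 200 × (1 − m) × 0.50.

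| m (assumed) | Patients | Responders | Per covariate (k = 10) |
|---|---|---|---|
| 0% | 200 | 100 | 10 |
| 10% | 180 | 90 | 9 |
| 20% | 160 | 80 | 8 |
| 30% | 140 | 70 | 7 |

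These losses apply to the term's own univariate model, and to the multivariate model if the term passes the 10% screen or is added on clinical grounds. Univariate models of the other factors lose nobody for this reason.

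**3. Treated patients outside the FAS.** The windows in SAP A1.1 assign any visit from Day 2 onward to Month 3, 6 or 12. A patient first seen again at Month 12 can therefore be in the FAS and is scored a Month 6 non-responder. Only patients with no post-baseline set at any time are excluded.

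Illustration: 50% response in the FAS (the rate in Protocol 9.5). Assumed: a factor present in 40% with OR 0.67, which gives 54.0% response without it and 44.0% with it.
- Early loss of 2%: all-treated response 0.98 × 50% = 49.0%.
- Early loss of 5%: 0.95 × 50% = 47.5%.
- OR at 5% loss, equal in both groups: rates become 51.3% and 41.8%, so OR = (0.418/0.582) / (0.513/0.487) = 0.682.
- OR at 5% loss, twice the risk with the factor: losses are 3.57% and 7.14%, rates 52.1% and 40.9%, and the OR is 0.636. At 2% loss it is 0.657.

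For scale, the standard error of the log OR with 120 and 80 patients is √[1/(120 × 0.54 × 0.46) + 1/(80 × 0.44 × 0.56)] ≈ 0.29. The shift from 0.67 to 0.636 is |ln(0.636/0.67)| / 0.29 ≈ 0.18 standard errors.

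**4. DAS28 after stopping.** SAP 6.1.1, 7 and A1.1 score Month 6 without reference to treatment status, so the default is DAS28 as observed. With 5% switching and 30% of switchers in LDA on the next drug (both assumed), response is 0.95 × 50% + 0.05 × 30% = 49.0% as observed. It is 47.5% if stopping counts as non-response.

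**5. The two imputation rules.** Assumed patient: at Month 3, TJC 1, SJC 1, CRP 5 mg/L and PtGA 30 mm, giving DAS28-4 (CRP) = 2.87. At Month 6 only PtGA 50 mm is recorded. Under SAP 7 the score is 0.56 + 0.28 + 0.36 × ln 6 + 0.014 × 50 + 0.96 = 3.15, which is LDA. Under a literal reading of Protocol 9.7.3.1 the patient is a non-responder. The difference arises whether or not tofacitinib was stopped.

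**The case against.** The sponsor could reply that the two Month 3 terms are only candidates, which selection may drop, and that losses will be slight. Protocol 9.5 says "It is expected that the amount of missing data and drop-outs will be minimal in this study". The first part stands as a limit on size: the responder counts in the table hold only for models in which a term is entered. It does not make a Month 3 change a baseline parameter.

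On the population, the FAS is defined identically in both documents, the windows admit almost any return visit, and the illustrated shift is a small fraction of a standard error. That stands, and it is why this is a secondary point. A reader might infer that the FAS biases the odds ratios or materially inflates response. The documents do not support that: they give no rate of early loss, and the direction of the effect on an odds ratio depends on whether loss differs by predictor level. Relative to counting these patients as non-responders, leaving them out cannot lower the response rate, but the size is unknown.

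A reader might also infer that the Month 6 endpoint is undefined once tofacitinib stops, or that follow-up is contradictory because Protocol 9.1 and SAP 2.1 end it at discontinuation. Neither follows. The scoring can be computed as written. Protocol 9.2 and 9.4.2.4 and SAP 2.2 continue follow-up through treatment changes, and SAP 8.2.1 plans listings for "patients who have discontinued Tofacitinib treatment but remain in the study". Discontinuation there most naturally means leaving the study. Treatment patterns are tabulated too (SAP 6.2 and 8.2.2), so readers will see how many patients switched.

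**Conclusion.** The Month 3 covariates are wrong as written. They conflict with the stated objective, with both descriptions of the primary analysis and with the SAP's declaration of no change. That conclusion rests on the text alone. The loss of responders to about 90, 80 or 70 rests on assumed missingness of 10%, 20% or 30%, and applies only to models containing the LDL or haemoglobin change.

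The FAS restriction is real but probably small, and is worth a sensitivity analysis rather than a new primary population. It would be too strong to say that the Month 3 terms cancel an all-treated analysis altogether. Nearly all the added patients would lack Month 3 values, but they would drop out only from models that include those terms.

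The treatment-status target, the meaning of discontinuation and the difference between the two imputation rules are matters of clarification.

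**What to change.** 1. In SAP 6.4, use baseline LDL and haemoglobin in the models for remission and LDA at Months 6 and 12. Move the Month 3 changes to a separate exploratory model, labelled as such. The change scores already require the baseline values, although Protocol 9.4.2.1 lists only blood biochemistry and haematology without naming these tests. The cost is SAP wording. State a rule for missing covariates at the same time.
2. Add an NRI sensitivity analysis in all treated patients (the Safety Analysis Set) for the same four outcomes. Define a set of post-baseline measurements. Report the number, baseline profile and withdrawal reasons of treated patients outside the FAS. The cost is four further model runs and possibly a lower response rate. NRI is itself an assumption that can move odds ratios. Refitting the covariates chosen in the primary models would keep differences in selection out of the comparison.
3. Clarify in wording that the Month 6 target is DAS28 regardless of treatment status. Scoring discontinuation as non-response can be an optional sensitivity analysis, using the date already derived in SAP 6.2. It would mix inefficacy with intolerance and administrative stops.
4. Reconcile discontinuation in Protocol 9.1 and SAP 2.1 with Protocol 9.2 and 9.4.2.4 and SAP 2.2. Reconcile the imputation rule in Protocol 9.7.3.1 with SAP 7.

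None of this needs new data. Added as sensitivity analyses, items 2 and 3 leave the primary definition unchanged. Changing the primary population or responder definition may need a protocol amendment under Protocol 9.7.
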